11.4.2. Collecting Adverse Events

AEs (including SAEs) may be discovered through any of these methods:

- Observing the participant
- Interviewing the participant (e.g., using a checklist, structured questioning, diary, etc.)
- Receiving an unsolicited complaint from the participant

11.4.3. Recording Adverse Events

Throughout the study, the investigator will record all AEs and SAEs as described previously on the appropriate AE/SAE eCRF regardless of the relationship to study therapy regimen or study procedure. Once recorded, an AE will be followed for 30 days, or until it resolves with or without sequelae, or until 30 days after the participant prematurely withdraws (without withdrawing consent)/or is withdrawn from the study, whichever occurs first. Once recorded, an SAE will be collected until the event is considered chronic and/or stable.

11.5. Reporting of Adverse Events and Pregnancy

This section describes the responsibilities of the site investigator to report SAEs, AESIs, and pregnancies to the FDA and the Sponsor. Timely reporting of AEs is required by 21 CFR and ICH E6 guidelines.

Serious Adverse Events and Adverse Events of Special Interest

All SAEs and AESIs, regardless of assessment of causal relationship or expectedness, must be reported by the site investigator to the Sponsor (or designee) within 24 hours of becoming aware of the event. Refer to the Manual of Procedures for the procedure to be followed.

For SAEs and AESIs, all requested information on the SAE CRF will be provided (**Appendix 3**). However, unavailable details of the event will not delay submission of the known information. As additional details become available, the AESI/SAE CRF will be updated and submitted.

Unexpected Non-Serious Adverse Events

An unexpected, non-serious adverse event that is of Grade 2 severity or higher **and** study related will be recorded and reported to the Sponsor under the SAE reporting procedure above (i.e. within 24 hours).

Pregnancy

Although pregnancy is not considered an AE, it is the responsibility of the investigator to report to the sponsor (or designee), within 24 hours of identification, any pregnancy occurring in a female or female partner of a male, during the study or within 60 days of the last dose of study drug. A pregnant subject shall be instructed to stop taking study medication. The investigator shall counsel the subject and discuss the risks of continuing with the pregnancy and the possible effects on the fetus. Monitoring of the pregnant subject shall continue until the conclusion of the pregnancy and the outcome of each must be reported.

Information requested about the delivery shall include:

- Gestational age at delivery
- Birth weight, length, and head circumference
- Gender
- Appearance, pulse, grimace, activity, and respiration (APGAR) score at 1 minute, 5 minutes, and 24 hours after birth, if available
- Any abnormalities.

Any complication to pregnancy such as a congenital abnormality or birth defect shall be submitted as an SAE to the sponsor using the SAE reporting procedures described above and to the FDA.

11.5.1. Reporting to the Health Authorities

The Sponsor has the responsibility of reporting all AEs and SAEs to the FDA within the reporting time limits set forth by the FDA.

1. Standard Reporting (IND Annual Report)

This option applies if the AE is classified as one of the following:

- Serious and expected SARs (see **Section 11.2.2**)
- Serious and not a suspected adverse reaction
- Pregnancy

Note that all adverse events (not just those requiring 24-hour reporting) will be reported in the Annual IND Report.

2. Expedited Safety Reporting

This category is required if the safety event is classified as one of the following:

- a. Serious and unexpected suspected adverse reaction [SUSAR]:*

The Sponsor shall report any SAR that is both serious and unexpected. The Sponsor shall report an SAE as a SAR only if there is evidence to suggest a causal relationship between the study drug and the SAE, such as:

- A single occurrence of an event that is uncommon and known to be strongly associated with drug exposure
- One or more occurrences of an event that is not commonly associated with drug exposure, but is otherwise uncommon in the population exposed to the drug
- An aggregate analysis of specific events observed in a clinical trial (such as known consequences of the underlying disease or condition under investigation or other events that commonly occur in the study population independent of drug therapy) that indicates those events occur more frequently in the drug treatment group than in a concurrent or historical control group

- b. Any new findings from studies that suggests a significant human risk*

The Sponsor shall report any findings from other clinical, epidemiological studies, pooled analysis of multiple studies, or any finding from animal or in vitro testing (e.g. mutagenicity, teratogenicity, carcinogenicity) that suggest a significant risk in humans exposed to the drug that would result in a safety-related change in the protocol, informed consent, investigator brochure, package insert, or other aspects of the overall conduct of the study.

SUSARs must be reported to the FDA within 15 calendar days; fatal or life threatening events must be reported to the FDA as soon as possible, but no later than 7 calendar days. To report a SUSAR, a finalized, initial SAE case report form and a MedWatch 3500A form will be generated by the site PI.

11.5.2. Reporting to IRBs/IECs

The investigator shall report AEs and SAEs in a timely fashion to their local and central IRB, if applicable, in accordance with applicable regulations and guidelines.

12. CLINICAL MONITORING STRUCTURE

12.1. Site Monitoring Plan

The study monitor and/or designee from Stanford will visit each site prior to enrollment of the first subject, and periodically during the study as per GCP and GMP. Every effort will be made to maintain the anonymity and confidentiality of subjects during this clinical study; however, because of the experimental nature of this treatment, the investigator agrees to allow representatives of the DSMB and authorized employees of the appropriate regulatory agencies and the Sponsor to inspect the facilities used in this study and to inspect, for purposes of verification, the hospital or clinic records of all subjects enrolled into this study.

12.2. Study Monitoring Plan

The investigators will work with the independent DSMB. The DSMB will meet every 6-12 months, or earlier if needed, to review safety data including all reported AEs and SAEs, as well as major and non-major deviations.

12.3. Protocol Amendments

The sponsor (Stanford) may not implement a change in the design of the protocol, assent or ICF without an IRB-approved amendment at Stanford, Mayo, and Phoenix Children's.

12.4. Protocol Deviations

The Sponsor will consider any deviations from the protocol on a case-by-case basis. The investigator or other health professional in attendance must contact the Sponsor as soon as possible to discuss the associated circumstances. The principal investigator (with the DSMB panel if needed) will then decide whether the subject should continue to participate in the study. All protocol deviations and the reasons for such deviations must be noted on the appropriate page of the subject's CRF and recorded on a protocol deviation log (**Appendix 4**).

A protocol deviation is any noncompliance with the clinical trial protocol, Good Clinical Practice (GCP), or Manual of Procedures requirements. The noncompliance may be either on the part of the subject, the investigator, or the study site staff. As a result of deviations, corrective actions are to be developed by the site and implemented promptly.

These practices are consistent with Good Clinical Practice (GCP ICH E6) Sections:

- Compliance with Protocol (Sections 4.5.1, 4.5.2, and 4.5.3)
- Quality Assurance and Quality Control (Section 5.1.1)
- Noncompliance (Sections 5.20.1 and 5.20.2.)

It is the responsibility of the site to use continuous vigilance to identify and report deviations according to the guidelines of the Sponsor. Protocol deviations will be sent to each local IRB/IEC per their guidelines and policies. The site PI/study staff is responsible and adhering to their central IRB reporting requirements.

12.5. Premature Termination of the Study

The sponsor has the right to terminate the study prematurely. Reasons may include efficacy, safety, or futility, among others. Should the sponsor decide to terminate the study, the investigator(s) will be notified in writing.

12.6. Close-out of a Site

The sponsor and the investigator have the right to close-out a site prematurely.

Investigator's Decision

The investigator must notify the sponsor of a desire to close-out a site in writing, providing at least 30 days' notice. The final decision should be made through mutual agreement with the Sponsor. Both parties will arrange the close-out procedures after review and consultation.

Sponsor's Decision

The Sponsor will notify the investigator(s) of a decision to close-out a study site in writing. Reasons may include the following, among others:

- The investigator has received all items and information necessary to perform the study, but has not enrolled any subject within a reasonable period of time
- The investigator has violated any fundamental obligation in the study agreement, including but not limited to, breach of this protocol (and any applicable amendments), breach of the applicable laws and regulations, or breach of any applicable ICH guidelines
- The total number of subjects required for the study are enrolled earlier than expected

In all cases, the appropriate IRB and Health Authorities must be informed according to applicable regulatory requirements, and adequate consideration must be given to the protection of the subjects' interests.

13. STATISTICAL ANALYSIS PLAN

This section provides the basis for the statistical analysis plan (SAP) for the study. The SAP may be revised during the study to accommodate amendments to the clinical study protocol and to make changes to adapt to unexpected issues in study execution and data that may affect the planned analyses. The final SAP will be issued before the database is locked and unblinded.

13.1. Statistical Hypothesis

The primary efficacy endpoint is the proportion of subjects who tolerate a cumulative dose of at least 2040 mg milk protein during a DBPCFC at week 18. The comparison between the dupilumab plus milk OIT arm (Cohort A) and the placebo plus milk OIT (Cohort B) arm will be made.

Letting p_D (and p_P) be the true proportion of subjects who tolerate a cumulative dose of at least 2040 mg milk protein during a DBPCFC at week 18 in the treatment arms of dupilumab + milk OIT and placebo + milk OIT, respectively. The following hypothesis for the superiority testing will be tested at the 5% 2-sided significance level:

$H_0: p_D = p_P$, i.e. the proportion of subjects who tolerate a cumulative dose of at least 2040 mg milk protein during a DBPCFC at week 18 is the same between dupilumab + OIT arm and the placebo + OIT arm

against the alternative

$H_a: p_D \neq p_P$, i.e. the proportion of subjects who tolerate a cumulative dose of at least 2040 mg milk protein during a DBPCFC at week 18 are different between the dupilumab + OIT arm and the placebo + OIT arm

13.2. Justification of Sample Size

It is assumed that the proportion of subjects who tolerate a cumulative dose of at least 2040 mg milk protein during a DBPCFC at week 18 will be 20%, based on prior data, with the proportion of patients in the dupilumab + OIT arm assumed to be 55%, which is considered to be a clinically meaningful benefit by adding on dupilumab treatment. A sample size of approximately 88 subjects (44 in dupilumab + OIT and 44 in placebo + OIT) will have 90% power to detect the treatment difference of 35% between placebo + OIT and dupilumab + OIT at the 2-sided 5% significance level. Assuming a 25% drop out rate, we will enroll 58 in each arm. The sample size calculations were done by Fisher exact test using SAS (version 9.4, Cary, NC).

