13.3. Analysis Sets

13.3.1. Efficacy Analysis Sets

The efficacy analyses will use the intention-to-treat population. The full analysis set (FAS) includes all randomized subjects. Efficacy analyses will be based on the treatment allocated at randomization (as randomized).

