13.5.1. Primary Efficacy Analysis

The primary endpoint will be analyzed using the Cochran-Mantel-Haenszel (CMH) test adjusted by randomization stratification factor (study site) to assess the treatment difference in the proportion of responders in the FAS. Estimate of treatment difference, p-value, and the 2-sided 95 % confidence interval will be calculated.

If a subject withdraws from study, the subject will be counted as a non-responder at time points after study withdrawal. The subject will also be considered a non-responder at the time point when data are missing. All observed data will be used for primary analysis.

Sensitivity analyses utilizing alternative methods for handling missing data will be performed to assess the robustness of the primary analysis result. Alternative methods may include complete case analysis (observed value analysis). Details will be specified in the statistical analysis plan (SAP).

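### Section 13.2's 35-point difference and 90% power do not describe the primary analysis, which keeps dropouts as non-responders and leaves baseline tolerated dose unused

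*Combined protocol and SAP*

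**What the plan says.** - **Sample size (13.2).** With assumed week 18 responder rates of 20% on placebo and 55% on dupilumab, 44 per arm "will have 90% power to detect the treatment difference of 35% between placebo + OIT and dupilumab + OIT" at two-sided 5%. "The sample size calculations were done by Fisher exact test". The number is then raised: "Assuming a 25% drop out rate, we will enroll 58 in each arm".
- **Hypothesis (13.1).** The two proportions are defined as true proportions "in the treatment arms of dupilumab + milk OIT and placebo + milk OIT, respectively", without restriction to completers.
- **Analysis set (13.3.1).** "The full analysis set (FAS) includes all randomized subjects".
- **Primary analysis (13.5.1).** A CMH "test adjusted by randomization stratification factor (study site"). On losses: "If a subject withdraws from study, the subject will be counted as a non-responder at time points after study withdrawal", and "The subject will also be considered a non-responder at the time point when data are missing".
- **Secondary analysis (13.5.2).** The ANCOVA of change in cumulative tolerated dose (CTD) adjusts for site and for the baseline tolerated dose.
- **Interim (13.8).** One look once 40 participants have completed their week 18 challenges, at an information fraction of 40/88.

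**The concern.** Dividing by one minus the dropout rate is right when dropouts vanish from the analysis and the rest respond at the assumed rates. In this primary analysis nobody vanishes: a dropout stays in the denominator as a failure. Dropout therefore acts on the response rates, not on the sample size. Section 13.2 does not say which kind of rate 55% and 20% are. The wording of 13.1 suggests all-randomised rates; the inflation suggests completer rates. On neither reading does the pairing of 35 points with 90% power belong to the analysis that will be run.

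Once dropout is part of the outcome, a difference in dropout between arms changes power, and 13.2 does not consider this. It is relevant here: Section 1.1 reports that roughly 20 to 30% of patients cannot complete milk up-dosing, and Section 1.2.1 plans to compare drop-out rates between arms.

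A separate matter is precision. Every randomised subject has a screening challenge, so the baseline tolerated dose is known for all, yet the primary test adjusts for site only.

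**Working it through.** **Inputs.** From 13.2: 55%, 20%, two-sided 5%, 44 and 58 per arm, 25% dropout. From 13.3.1 and 13.5.1: all randomised subjects, non-responder imputation, CMH. The unequal dropout splits and the prognostic strength of baseline dose are not in the documents and are assumed.

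**Method.** Exact enumeration over two binomials. With *x* and *y* responders out of *n* per arm, *m = x + y* and *N = 2n*, the Mantel-Haenszel statistic is Z = (x − m/2) / √[n²m(N − m) / (N²(N − 1))]. The continuity-corrected form takes 0.5 off |x − m/2|. Power is the total probability of outcomes with |Z| ≥ 1.96. Site strata and the interim look are ignored.

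**Step 1: the plan's own figures.** At 44 per arm, Fisher power is 90.8%, so the stated 90% reproduces. 44/0.75 = 58.7 and 58 × 0.75 = 43.5, so 58 leaves about 44 evaluable per arm. The interim boundary also reproduces: at 40/88 the O'Brien-Fleming-type spending function gives alpha 0.0018 and Z 3.13.

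**Step 2: the primary analysis at 58 per arm.** On the completer reading, the rates tested are 0.55 × (1 − dropout) and 0.20 × (1 − dropout), with all dropout before week 18.

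| Reading, dropout dupilumab/placebo | Rates tested | Difference (points) | Fisher | CMH | CMH, corrected |
|---|---|---|---|---|---|
| 55%/20% already count dropouts | 55% vs 20% | 35 | 96.8% | 97.9% | 96.6% |
| Completer, 20/20 | 44% vs 16% | 28 | 89.2% | 92.4% | 88.5% |
| Completer, 25/25 | 41.25% vs 15% | 26.25 | 86.0% | 89.9% | 85.1% |
| Completer, 30/30 | 38.5% vs 14% | 24.5 | 82.2% | 86.9% | 81.1% |
| Completer, 20/30 | 44% vs 14% | 30 | 93.8% | 95.9% | 93.4% |
| Completer, 30/20 | 38.5% vs 16% | 22.5 | 73.4% | 79.4% | 72.0% |

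The uncorrected CMH test at 58 per arm has 90% power for 41.3% vs 15% (26 points) or 47.9% vs 20% (28 points).

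**Step 3: timing of dropout.** If only three quarters of the 25% leave before week 18 (18.75% per arm), uncorrected CMH power on the completer reading is 92.9%. If half do (12.5% per arm), it is 95.1%.

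**Step 4: baseline adjustment.** The screening doses are 1, 3, 10, 30, 100 and 300 mg, and an eligible subject must react by 444 mg cumulative. The possible baseline CTDs are therefore 0, 1, 4, 14, 44 and 144 mg. Simulation: 20,000 trials per case, 58 per arm, three sites, the six values assumed equally likely, dose entered as log(dose + 1). Entries are CMH power → adjusted power (%).

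| Odds ratio per SD | 25/25, baseline predicts the counted outcome | 25/25, dropout unrelated to baseline | 30/20, baseline predicts the counted outcome | 30/20, dropout unrelated to baseline |
|---|---|---|---|---|
| 1 | 89.7 → 89.1 | 89.8 → 89.3 | 79.6 → 79.0 | 78.7 → 78.0 |
| 1.5 | 89.8 → 90.3 | 89.8 → 89.9 | 79.7 → 80.2 | 79.2 → 79.4 |
| 2 | 89.9 → 91.8 | 89.9 → 91.0 | 79.4 → 82.0 | 79.2 → 80.6 |
| 3 | 90.0 → 94.4 | 89.6 → 92.6 | 79.1 → 85.5 | 78.9 → 82.8 |

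With all-randomised rates of 55% vs 20%, the largest gain is 1.4 points (97.9 → 99.3). Under the null with both looks, overall rejection was 0.047 to 0.052 for CMH and 0.044 to 0.051 for the adjusted test. At the interim alone the adjusted test rejected 0.0006 to 0.0015 of the time, against a nominal 0.0018.

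**The case against.** **A reader might infer that the sample size arithmetic is wrong or the trial underpowered.** Neither is supported. The 90% at 44 per arm and the step to 58 both reproduce. On the planned test, uncorrected, power at equal 25% dropout is still about 90%, and higher if some subjects leave after week 18. Section 6.5.2 also asks those who stop study drug without withdrawing to attend remaining visits, which softens the dilution further. Sizing by Fisher and testing by CMH is not a defect.

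**A reader might infer that the inflation is wasted if the rates already count dropouts.** That holds for the primary test only. Section 13.5.4 puts the week 18 change in CTD inside the alpha hierarchy, and 13.5.2 first says that missing week 18 continuous data are not imputed. Dropouts do leave that analysis, and the complete-case sensitivity analysis too. (A later paragraph of 13.5.2 applies LOCF to some of these subjects, which sits uneasily with the first rule.)

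**A reader might take 79% as the expected power.** The protocol expects dupilumab to improve tolerability (Sections 1.1, 1.2.1 and 2.1), so the direction it suggests is less loss on dupilumab, the 96% case. The 30/20 split is a stress case. The continuity-corrected figures likewise rest on a version of the test that 13.5.1 neither names nor rules out.

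**On baseline dose,** a CMH test stratified by the randomisation factor is valid, and an ANCOVA of change has its own reason to include baseline. The gain cannot be computed from the documents, and eligibility restricts baseline to 0 to 144 mg, which may limit its prognostic value. All of this stands.

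What remains is that the difference and power in 13.2 are not jointly those of the primary analysis on either reading, and that data already in hand go unused.

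**Conclusion.** The point holds as a mismatch between the inflation and the primary analysis. With all-randomised rates, 58 per arm gives about 98% power for 35 points. With completer rates and equal 25% loss before week 18, it gives about 90% (85% corrected) for 26 points. Assumed unequal dropout spans 79% (30% dupilumab, 20% placebo) to 96% (20% and 30%) on the completer reading. These are single-stratum figures that ignore the interim.

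The omission of baseline tolerated dose is a missed efficiency, not an error. At 25/25 it is worth about 0 to 4 points of power for assumed odds ratios of 1.5 to 3 per SD, and costs up to about 1 point if baseline is not prognostic.

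Both should be settled before the interim. Neither is a reason to change enrolment.

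**What to change.** 1. **Section 13.2.** State whether 55% and 20% count dropouts as failures. Restate the difference and power for the analysis to be run: all randomised subjects, 58 per arm, non-responder imputation, CMH, naming whether it is continuity-corrected. Give equal and unequal dropout as sensitivity cases. In **13.8**, state how subjects withdrawn before the interim are counted: the look is triggered by completed week 18 challenges, whereas 13.5.1 counts withdrawals as failures.
2. **Section 13.5.1, before the interim.** Specify that the primary analysis adjusts for baseline CTD and site through a logistic model, reporting a standardised risk difference with a small-sample-corrected standard error. Enter the dose as log(dose + 1) or ordered categories, because a baseline of 0 mg is possible and log(0) is undefined. Use the same test at both looks, name CMH as the fallback if the model does not converge, and keep CMH as supportive.

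**Cost.** Wording in 13.2, 13.5.1 and 13.8. Section 13 allows SAP revision until database lock, but item 2 must precede the first unblinded look. Item 2 risks up to about 1 point of power, a slightly conservative test at 20 per arm, possible non-convergence there, and a little more analysis work. On the completer reading the stated difference becomes smaller. No extra patients, visits or data are needed.

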13.3. Analysis Sets

13.3.1. Efficacy Analysis Sets

The efficacy analyses will use the intention-to-treat population. The full analysis set (FAS) includes all randomized subjects. Efficacy analyses will be based on the treatment allocated at randomization (as randomized).

13.3.2. Safety Analysis Set

The safety analysis set (SAS) includes all randomized subjects who received any study drug; it is based on the treatment received (as treated). Treatment compliance/administration and all clinical safety variables will be analyzed using the SAS.

13.4. Statistical Methods

For continuous variables, descriptive statistics will include the following information: the number of subjects reflected in the calculation (n), mean, median, first quartile (Q1), third quartile (Q3), standard deviation, minimum, and maximum.

For categorical or ordinal data, frequencies and percentages will be displayed for each category.

All data will be summarized by treatment groups as outlined below: Placebo plus milk protein OIT vs dupilumab plus milk protein OIT.

